There will be a Data Safety and Monitoring Board (DSMB) for this study composed of three investigators who have experience in clinical research, clinical treatment of BD, and specifically overseeing the safety of participants in bipolar trials. This DSMB will monitor safety issues, including the review of adverse events, the PI's quarterly report of the study's progress, all IRB amendments, the adequacy and integrity of accumulating data, and the capability of the Phase I and II trials to test the hypotheses. The purpose of this process is to assess scientific integrity and patient safety issues, and ensure the ethical conduct of the trials. The DSMB will approve the initiation of the study and subject enrollment, and determine if study procedures should be altered or stopped due to evidence of benefit or harm to trial subjects that may be attributable to NEW Tx or reasons related to scientific integrity. The PI will submit quarterly reports to the DSMB detailing any study changes, adverse events, subject recruitment and retention, reasons for early termination, and ongoing data reports. The PI will also respond to all DSMB issues and queries.

B. Adverse Events

Any serious adverse events (e.g., death, suicide attempt, hospitalization) will be reported within 24 hours to the IRB and the NIMH program officer. A full written report of the event will be sent to the above entities within 10 working days of the event's occurrence. All adverse events will be assessed for the events' severity/intensity, expectedness, relatedness to NEW Tx, clinical outcome, and any action taken due to the event. Any adverse event (e.g., causing interference with usual activities or requiring treatment) and which appears definitely, probably, or possibly related to study participation will be tracked and reported to the IRB at the yearly continuing review. Any serious adverse events will be summarized in the NIMH, DSMB, and IRB annual progress reports. We will also inform the NIMH, DSMB and the IRB of actions, if any, as a result of their continuing review.

VIII. DATA ANALYSIS

Baseline demographic and clinical characteristics will be examined by the PI in collaboration with [name]., Professor of Biostatistics. Measures of central tendency and variability will be estimated on each continuous measure; proportions estimated for categorical variables. Transformations will be used when distributional assumptions are not fulfilled for inferential tests. Dropouts and completers will be compared on baseline variables using Mann-Whitney or chi-square tests.

A. Data Management: REDCap

To ensure the quality of electronic data capture (EDC) and management, the data management team will use the REDCap EDC system. The REDCap Consortium is comprised of 135 active institutional partners and it supports two secure, web-based applications (REDCap and REDCap Survey) designed to support data capture for research studies. The REDCap application is currently in production use or development build-status for more than 2990 studies with over 9540 end-users spanning numerous research focus areas across the consortium, and the REDCap Survey application is now being adopted rapidly by consortium partners. Both REDCap and REDCap Survey provide a process for building a database or online survey, an interface for collecting data, data validation, and automated export procedures for data downloads to statistical packages (SPSS, SAS, Stata, R).

REDCap allows users to design and implement study scales to collect, store, retrieve, and manipulate data electronically. The REDCap platform for EDC that streamlines data collection and management, and the system is a study management tool used to monitor visit timing and completion in real-time, thus helping to minimize missing data. REDCap is already used at MGH for treatment studies and has proved extremely useful for conducting and managing studies. It obviates the need for data entry by staff, thus minimizing cost and human error. Furthermore, because data quality control checks can be built into the logic of the online measures, problems can be identified in real-time, thereby improving data quality and consistency.

Research staff will enter scale and assessments responses into the REDCap electronic assessment forms. Using 128 bit RSA Secure Socket Layer (SSL) encryption, approved users will be logged-in to machines using secured browsers behind the Partners Healthcare Systems IS corporate firewall or the RIH firewall. Staff will have a unique identifying key that will link them to the electronic study forms. This unique ID will be used in addition to a randomly generated secure password that only the staff person will have. Additional confidentiality procedures are detailed in the Human Subjects section.

B. Statistical Analyses Plan for Research Aims

Each of the statistical tests below will use a two-tailed alpha-level of 0.05.

- i. **Aim 1: Feasibility in Nonrandomized Trial (Phase I).** *Hypothesis 1a:* Descriptive statistics will be used to report the number of intervention sessions attended (we expect > 80%), number of participants recruited per month, and therapist adherence to NEW Tx (average adherence score ≥ 6). *Hypothesis 1b:* Participants will report high satisfaction (total CSQ-8 score, $M > 24^{75}$) with the treatment and acceptability (total NEW Tx Scale score, $M < 25$, or at least an average score of “agree” on half of the items).
- ii. **Aim 2: Feasibility in Randomized Trial (Phase II).** *Hypothesis 2a:* Descriptive statistics will be used to report the number of intervention sessions attended (we expect > 80%), number of participants recruited per month, randomization rate (number randomized/number consented), number of assessment sessions attended (we expect > 80%), and retention (number of study completers/number randomized) (we expect > 80%, which is conservative for diet and exercise interventions for severe mental illness^{25, 76-78}) and therapist adherence to NEW Tx (average adherence score ≥ 6). *Hypothesis 2b:* Participants will report high expectations (CEQ score) for the treatment and high satisfaction and acceptability (CSQ-8, Post-Tx Questionnaire, NEW Tx Scale).
- iii. **Aim 3: Exploratory Aims (Phase II).** *Hypotheses 3a and 3b:* Between treatment group effects sizes (and 95% CI) will be calculated. To supplement this, Mann-Whitney tests will compare treatment groups on medical burden (as measured by FRS) (*Hypothesis 3a*) and on improvement in symptoms (MADRS, YMRS) and functioning (LIFE-RIFT) (*Hypothesis 3b*) based on change from baseline. *Hypothesis 3c.1:* We will investigate baseline BMI as a potential moderator of treatment response. The focus will be on the magnitude of the effect, not on significance testing. The between treatment group effect sizes (i.e., FRS, MADRS, YMRS, LIFE-RIFT) will be compared with those who have high baseline BMI (> 30) versus low BMI (< 30). *Hypothesis 3c.2:* Mastery of the diet (Nutrition Data System score of food diaries) and exercise (weekly exercise duration from Exercise Questionnaire) modules will mediate the association of NEW Tx and improvement in medical burden (FRS). The

dependent variable will represent change in the FRS score from time of completion of respective module. The mediators will be tested separately. Differential between treatment group effect sizes for those who did and did not master the modules will provide evidence of a mediator of treatment.

C. Rate of Attrition

Some attrition (i.e., 20%) is expected and this can result in bias and reduce power, precision and generalizability⁷⁹. Consistent with the Intent to Treat principle⁸⁰, we will continue with the assessments for the study duration, even among those who fail to comply with the treatment⁸¹. As one aspect of the feasibility study, we will assess the likelihood to attrite using the “Intent to Attend” measure⁷².

D. Power Analysis

The sample sizes for the Phase I and II trials are based primarily on the fundamental aim of this project: feasibility. The N is not based on what is needed for inferential analyses as they are not a fundamental aspect of the design. Power analyses are not indicated for the proposed exploratory analyses. We acknowledge that we will not have sufficient power to detect large effects (e.g., $d = .80$).

IX. REFERENCES

1. Hennekens C. Increasing global burden of cardiovascular disease in general populations and patients with schizophrenia. *Journal of Clinical Psychiatry*. 2007;68(suppl 4):4-7.

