- i. **Aim 1:** Feasibility and Acceptance of NEW Tx in the Nonrandomized Trial (N=6). *Hypothesis 1a:* A preliminary study of whether NEW Tx will be feasible with regards to recruitment, retention, blinded assessments, and therapist adherence to NEW Tx⁴³. *Hypothesis 1b:* Participants will report high satisfaction with the treatment (CSQ-8) and acceptability (NEW Tx Scale) over the study duration (i.e., 20-weeks) in a nonrandomized trial ($n = 6$).
- ii. **Aim 2:** Feasibility and Acceptance of NEW Tx and its Evaluation in the Randomized Pilot Trial ($n = 40$). *Hypothesis 2a:* A pilot study of whether NEW Tx will be feasible with regards to recruitment, randomization, retention, blinded assessments, and therapist adherence to NEW Tx⁴³. *Hypothesis 2b:* Participants will report high expectations for the treatment (CEQ) and high satisfaction and acceptability with the treatment (CSQ-8; Post-Tx Questionnaire; NEW Tx Scale) in a 20-week nonrandomized trial ($n = 6$).

B. Exploratory Aims

- i. **Aim 3a:** Reducing Medical Burden in the Randomized Pilot Trial. Pilot test ($n = 40$) the efficacy of NEW Tx in improving medical burden using the Framingham Risk Score (FRS). *Hypothesis 3a:* Over the course of 20-weeks (18 sessions) the NEW Tx group will have a lower FRS compared to treatment as usual (TAU) in the randomized pilot trial.
- ii. **Aim 3b:** Symptoms and Functioning in the Randomized Pilot Trial. Examine the efficacy of NEW Tx in improving functioning and symptoms of BD. *Hypothesis 3b:* Over the course of 20-weeks (18 sessions) the NEW Tx group will improved functioning (LIFE-RIFT) and symptoms (YMRS, MADRS) compared to TAU in the randomized pilot trial.
- iii. **Aim 3c:** Moderator and Mediator of NEW Tx in the Randomized Pilot Trial. Investigate a potential moderator and mediator of treatment response. *Hypothesis 3c.1:* Individuals with higher baseline BMI (>30) will moderate the between treatment effect size for medical burden (FRS) in the randomized pilot trial, such that of NEW Tx will have lower FRSs. *Hypothesis 3c.2:* Mastery of the diet (food diaries) and exercise (exercise duration from Exercise Questionnaire) modules of NEW Tx will mediate the association of NEW Tx and improvement in medical burden (FRS).

III. INTERVENTION MODULES AND OVERVIEW

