- ii. **Phase II:** In this phase, we will pilot test the NEW Tx methods compared to TAU ($n = 60$) to further examine feasibility, to estimate an effect size, and to explore its efficacy for reducing medical burden. TAU will be the control group in the Phase II pilot study as it is the standard treatment in the Massachusetts General Hospital (MGH) Bipolar Clinic and Research Program. Participants randomized to TAU who complete the first 20 weeks of the study will have the option to receive NEW Tx. TAU participants who chose to receive NEW Tx (the waitlist group) will follow the same procedures as the NEW Tx group over an additional 20 weeks such that they will have assessments at Weeks 30, (mid-treatment), 40 (post-treatment), and 52 (follow-up) (see Table 2). For TAU, medication and dosage changes are allowed as long as the change is recommended based on the guidelines and participants remain on a mood stabilizer. Medication changes will be monitored with the Clinical Monitoring Form Medication Module. All participants will have a three-month follow-up visit during which post-treatment measures and assessments will be repeated. Participants will be recruited with the same criteria as the nonrandomized trial, but will be randomized using a 1:1 allocation ratio with a blocking strategy. The assessments will be similar to those used in Phase I. In addition to the study staff utilized in Phase I, clinicians with training in CBT and mood disorders will be added as NEW Tx therapists.

B. Participant Selection and Recruitment

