Participants ($n = 6$ for the open trial phase; $n = 60$ for the randomized phase) will be recruited from within as well as outside the MGH Bipolar Clinic and Research Program, and we plan to recruit 1 participant per month for the Phase I open trial and 2 participants per month for the Phase II randomized trial. Some subjects will be self-referred, whereas others will be referred by MGH or community clinicians. Some subjects may be obtained from media advertisements. Potential participants will not be identified through medical records, and the researchers will not contact potential participants without their permission. If a clinician feels that one of his or her patients would be potentially appropriate for this study, the patient will be encouraged to contact the PI or the research assistant directly. Alternatively, the clinician may ask the patient to give permission to be contacted over the phone by either the PI or the research assistant. Written IRB approved informed consent will be obtained from all patients before protocol-specified procedures are carried out.

Patients may be referred to the study by their treating clinicians in the MGH Bipolar Clinic and Research Program, and will be recruited according to the following criteria:

i. **Inclusion Criteria**

- Diagnosis of Bipolar Disorder (Type I or II), which is the primary focus of treatment
- Ability to give informed consent
- Currently ill (CGI-BP ≥ 3)
- Age > 18 years and < 65 years
- Overweight individuals (BMI > 25); those with BMI of 25-30 must also have high rate of percentage of body fat (greater than or equal to 32% for women and 25% for men)

ii. **Exclusion Criteria**

- Unwilling/unable to comply with study procedures
- Endorsed item, confirmed by patient's physician, on the PAR-Q
- Euthymic (CGI-BP < 3)
- Diagnosis of anorexia nervosa or bulimia nervosa in the past month
- Diagnosis of substance dependence in the past month
- Active suicidality (MADRS item 9 score > 4)
- Pregnant (as analyzed by a urine pregnancy test)
- Exercising regularly (i.e., 5 days per week for 30 min)
- Neurologic disorder or history of head trauma
- Contraindications to exercise or diet interventions (e.g., co-morbid nutritional and metabolic diseases, physical injuries)

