The independent evaluators will receive instructions and observe the other trained independent evaluators in the BCRP, who have extensive experience in administering the study assessments.

E. Clinician Training

New therapists utilized in Phase II of the study will be trained by the PI. The therapists will be required to demonstrate understanding of the theoretical rationale for each module of NEW Tx, knowledge of BD, and proficiency in the strategies and techniques used to achieve treatment goals. Specific training components will include: (1) reviewing the procedures with PI; (2) role playing NEW Tx techniques; and (3) ongoing weekly supervision with the PI to review their sessions.

Some treatment sessions will be taped to ensure treatment integrity. The PI will review selected audio files and give feedback to the NEW Tx therapists. Audio recording is optional, so participants may opt out and still participate in the study. Audio files will be recorded with a microphone connected to a Partners computer. Files will be uploaded and saved directly to the BCRP secure network, they will not be saved as hard copies. Audio files will be labeled with the subjects' study IDs and not their names. Files will be sent to the PI through Partners Secure File Transfer (<http://rc.partners.org/sFTP>).

F. Targeted Enrollment

We expect to recruit a representative sample of Boston, MA, the location of our research site (see Table 3 and Table 4)⁷⁴. We expect that our sample will resemble the general population given that current studies in the MGH Bipolar Clinic and Research Program are meeting or exceeding this minority representation.

Table 3. Minority Representation in Boston, MA

Racial/Ethnic Category	Boston, MA*
Race	
White	76.1%
Black or African American	14.4%
American Indian and Alaska Native	0.4%
Asian	7.8%
Native Hawaiian and Other Pacific Islander	0.1%
Ethnicity	
Hispanic or Latino	10.5%
White Persons, Not Hispanic/Latino	68.1%
Other	21.4%

*Suffolk & Norfolk Counties

Table 4. Expected Enrollment by Race, Ethnicity and Gender

TARGETED/PLANNED ENROLLMENT for Phase I and II Studies (n = 60)				
Ethnic Category	Sex/Gender			
	Females	Males	Unknown or Not Reported	Total
Hispanic or Latino	6	6		12
Not Hispanic or Latino	18	18		36
Unknown (individuals not reporting ethnicity)	6	6		12
Ethnic Category: Total of All Subjects	30	30		60
Racial Categories				
American Indian/Alaska Native	0	0		0

Asian	3	3		6
Native Hawaiian or Other Pacific Islander	0	0		0

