Black or African American	4	4		8
White	23	23		46
More Than One Race				2
Unknown or Not Reported				6
Racial Categories: Total of All Subjects	30	30		60

V. POTENTIAL BENEFITS

Participants may be reimbursed for up to \$20/visit for travel-related costs as needed. Additionally, at two points during the 20 week treatment (one around midway and one around the end) participants will receive \$10, for a total of \$20, as part of their work with NEW Tx therapists to set and achieve treatment-related goals.

The proposed research study involves an intervention that holds the potential for direct individual benefit. This research will further our knowledge about medical burden in BD and the feasibility of psychosocial treatment to reduce this burden. Risks of discomfort associated with NEW Tx should be offset by the potential physical and mental health benefits. Thus, this study has the potential to not only improve the treatment of BD patients, but also advance the field by developing a treatment that can be used in future treatment studies of BD.

VI. RISKS AND DISCOMFORT

The risks that the Phase I and II trials pose to participants are reasonable in relation to the anticipated benefits because BD is associated with a disproportionately high medical burden as well as chaotic mood swings and a high rate of functional impairment. As the NEW Tx represents an augmentation of standard treatment with an experimental psychosocial intervention, the additional risk is small, justifiable given the potential benefits, and is at least as favorable as alternative approaches.

A. Potential Risks to Subjects

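### The Phase II randomised sample size is 40 in the aims but 60 in the design and recruitment sections, and Table 4's total for both phases fits neither.

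*Combined protocol and SAP*

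**What the plan says.** The randomised pilot is sized in five places in the combined protocol and SAP.

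- Section II.A, Aim 2 (heading): "Feasibility and Acceptance of NEW Tx and its Evaluation in the Randomized Pilot Trial ($n = 40").
- Section II.B, Aim 3a: "Pilot test ($n = 40$) the efficacy of NEW Tx in improving medical burden".
- Section IV.A.ii, Phase II design: "we will pilot test the NEW Tx methods compared to TAU ($n = 60").
- Section IV.B, recruitment: "n = 60$ for the randomized phase", beside six for the open trial, with planned accrual of "2 participants per month for the Phase II randomized trial".
- Section IV.F, Table 4 (heading): "TARGETED/PLANNED ENROLLMENT for Phase I and II Studies (n = 60").

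Hypothesis 2b sits under Aim 2, the randomised pilot, but its sentence ends "in a 20-week nonrandomized trial ($n = 6"). The analysis plan (Section VIII.B.ii) treats Hypothesis 2b as a Phase II hypothesis. Section VIII.D, where one would look for the planned number, says that sample size rests primarily on feasibility and gives no N.

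**The concern.** Each figure appears twice in running text, so a single slip of the pen does not explain the difference. All the passages belong to the same dated version, no amendment log is involved, and no sentence says which figure governs. Table 4 should settle the matter but adds a third reading.

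The planned number decides when Phase II recruitment is complete. It also sets how precisely the feasibility rates and the between-group effect sizes will be estimated, and Section IV.A.ii names estimating an effect size as a purpose of Phase II. Section VII.A gives the monitoring board quarterly reports on recruitment and retention and asks it to judge whether the trials can test their hypotheses. It cannot judge recruitment progress against two targets.

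**Working it through.** **Inputs.** Phase I: 6 (Sections II.A, IV.A.i, IV.B). Phase II: 40 (Section II) or 60 (Sections IV.A.ii, IV.B). Accrual: 2 per month (IV.B). Allocation: 1:1 (IV.A.ii). Retention benchmark: 80% (VIII.B.ii). Expected attrition: 20% (VIII.C). The plan gives no sample-size formula or power target, so neither N can be reproduced from its own inputs. What can be checked is whether the totals agree and what the difference amounts to.

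**Table 4 total.** 6 + 40 = 46 and 6 + 60 = 66; the table prints 60 for both phases. Taken literally, 60 in total implies 60 − 6 = 54 randomised, a number that appears nowhere.

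**Table 4 rows.** Ethnicity: 12 + 36 + 12 = 60, as printed. Race, as the table reads in the extracted text: 0 + 6 + 0 + 8 + 46 + 2 + 6 = 68, against 60 on the line "Racial Categories: Total of All Subjects". The rows split by sex do agree with that line: 0 + 3 + 0 + 4 + 23 = 30 for each sex, 60 in all. The excess of 8 is the two rows (2 and 6) with no entry by sex.

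**Recruitment time.** 40/2 = 20 months; 60/2 = 30 months.

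**Retention, if observed at 80%.** Wilson 95% interval, with p = 0.8 and z = 1.96: [p + z²/(2N) ± z√(p(1−p)/N + z²/(4N²))] / (1 + z²/N).

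- N = 40 (32/40): 0.652 to 0.895.
- N = 60 (48/60): 0.682 to 0.882.

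**Effect size.** The 95% half-width for a standardised difference d, with n per arm, is 1.96 × √(2/n + d²/(4n)). The values of n are 20 and 30 with complete data. After 20% attrition they are 20 × 0.8 = 16 and 30 × 0.8 = 24.

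| | N = 40 | N = 60 |
|---|---|---|
| d near 0, complete | 1.96√(2/20) = 0.62 | 1.96√(2/30) = 0.51 |
| d near 0, after attrition | 1.96√(2/16) = 0.69 | 1.96√(2/24) = 0.57 |
| d = 0.80, complete | 1.96√(0.100 + 0.008) = 0.64 | 1.96√(0.0667 + 0.0053) = 0.53 |
| d = 0.80, after attrition | 1.96√(0.125 + 0.010) = 0.72 | 1.96√(0.0833 + 0.0067) = 0.59 |

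**Can Section VIII.D identify the intended N?** It says power will be insufficient even at d = 0.80. For a two-sided 0.05 test at that effect, t-test power is 69% with 40 analysed, 77% with 48 (60 less 20%) and 86% with 60. A Mann-Whitney test simulated under normality (20,000 runs) gives 67%, 75% and 83%. The plan sets no threshold for sufficient power, so the sentence neither identifies the intended N nor is shown to be wrong.

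**The case against.** The best reply is that the two operational sections, design and recruitment, agree on 60, that recruitment is the section staff will follow, and that 40 appears only in the aims. On that view a target exists and the aims are out of date. This is fair as far as it goes: the target is contradicted rather than absent. Which figure is outdated remains an inference, because the document does not say.

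It can also be said that little depends on the number. The size is set for feasibility, efficacy is exploratory, and the attendance, randomisation and retention rates in Section VIII.B.ii use observed counts, so no definition or analysis changes with N. No recruitment deadline is stated that 30 months would breach. All of this stands and limits the seriousness of the point. The completion point for enrolment and the precision of the estimates still depend on N.

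Two side points deserve less weight. The race sum of 68 may reflect entries the printed total never meant to include, or columns displaced when the table was read, and it has no bearing on the Phase II number. Hypothesis 2b is a wording error that its own aim heading and the analysis plan already resolve.

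**Conclusion.** The inconsistency is real and should be fixed. The current text gives two Phase II targets 20 patients apart, and Table 4's combined total is 6 below one possible sum and 14 above the other.

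The practical size is moderate: 10 months of recruitment at the planned rate, a few percentage points at each end of the retention interval, and 0.11 to 0.13 in the half-width of the standardised difference. The calculations assume equal arms, the usual large-sample variance for d, retention observed at exactly 80%, and, where stated, attrition of 20% in each arm. The contradiction itself depends on none of these. The document does not show which N is intended, and this review does not infer one.

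**What to change.** The sponsor should choose one Phase II number and state it everywhere.

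- If it is 60: change Aims 2 and 3a to 60. Then either set Table 4's total to 66 or relabel the table as Phase II only.
- If it is 40: change Sections IV.A.ii and IV.B to 40 and set Table 4's total to 46, or relabel the table as Phase II only with a total of 40.
- In either case, check the race rows against the source table, and make the race and ethnicity rows both add to the stated total.
- In Hypothesis 2b, replace the reference to the nonrandomised trial of six with the 20-week randomised pilot and the chosen N.
- Optionally, name in Section VIII.D the N and the attrition to which the remark about d = 0.80 refers.

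These are corrections to text and one table. They add no visits or analyses, and no patients beyond whichever number the sponsor confirms.

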- viii. **Exercise Questionnaire** (EQ) is a modified version of the Exercise History and Attitude Questionnaire which has been used in a wide variety of settings^{63, 64}. It is typically administered to healthy populations; thus, some items were excluded that were not likely to pertain to BD. This questionnaire assesses baseline (i.e., past) exercise history as well as ongoing exercise duration and frequency at follow-up study visits⁶⁵.
- ix. **LIFE- Range of Impaired Functioning Tool** (LIFE-RIFT^{66, 67}) assesses the extent to which medical burden has impacted current functioning.
- x. **Framingham Risk Score** (FRS) will be used to estimate medical burden as it is designed to estimate risk in adults (age > 20) to predict 10-year risk for myocardial infarction and coronary death. The FRS is calculated

based on six indices: age, gender, total cholesterol, HDL cholesterol, smoker (Y/N), systolic blood pressure, and medications to treat high blood pressure (Y/N). It is one of the most widely validated and cited clinical prediction scores, and although several modifications have been proposed, a recent review of over 1900 studies found that these studies had “flaws in their design, analyses, and reporting that cast some doubt on the reliability of the claims for improved prediction”⁶⁸. The Medical History form will collect the patient data necessary to calculate the FRS score.

- xi. **Physical Activity Readiness Questionnaire (PAR-Q⁶⁹)** is a seven-item, self-report questionnaire to screen individuals for starting an exercise program. In addition to the PAR-Q, an EKG will be required for participants over the age of 40, if clinically indicated, to further minimize potential risks associated with exercising.
- xii. **Credibility/Expectancy Questionnaire (CEQ⁷⁰)** is a 6-item, self-report questionnaire to assess patients' perceptions of and expectations for treatment before the study begins.
- xiii. **Client Satisfaction Questionnaire-8 (CSQ-8⁷¹)** is a reliable and valid self-report of participants' acceptability of treatment. This is an assessment of client/patient satisfaction with their care and perceived quality and tolerability of NEW Tx.
- xiv. **NEW Tx Scale** is a 10-item scale to assess participants' acceptability of NEW Tx. This scale also includes a comments section to solicit unstructured feedback from participants on NEW Tx.

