ET= Early Termination. Vitals = Height (at Week 0 and Week 20), weight, waist circumference, blood pressure, pulse, and Dual X-Ray Absorptiometry (i.e., body composition). ** Includes lipid profile (i.e., cholesterol, triglycerides), metabolic panel (i.e., blood urea nitrogen (BUN), creatinine (Cr), electrolytes, blood glucose level), complete blood count (CBC), and thyroid stimulating hormone (TSH). C reactive protein (CRP) and inflammatory marker panels (Human TH1/TH2 10-Plex (IFN-g, IL-1b, IL-2, IL-4, IL-5, IL-8, IL-10, IL-12p70, IL-13, TNF-a)) will be included at pre- and post-treatment visits. A urine pregnancy test will be administered at Week 0 to determine eligibility. An EKG will be completed at Week 0 for participants \geq 40-years-old, if clinically indicated.

¹As needed.

†For the TAU group, will only be collected at Weeks 0, 10, and 20

Table 2. Schedule of Assessments for the Waitlist Group (TAU participants who choose to receive NEW Tx)Weeks	21	22	23	24	25	26	27	28	29	30	31	32	33	34	35	36	37	38	39	40	52
										Mid-tx									Post-tx	Follo w-up	
CGI-BP										x									x	x	
Blood Draw**										x									x	x	
Vitals										x									x		
DXA scan																			x		
CMF										x									x	x	
MADRS										x									x	x	
YMRS										x									x	x	
LIFE-RIFT										x									x	x	
NEW Tx Scale																			x	x	
CSQ-8																			x	x	
URICA	x																		x	x	
Met Cart	x																		x		
Post-Tx Questionnaire																			x	x	
EQ	x	x	x	x	x	x	x	x	x	x	x	x	x	x	x	x	x	x	x	x	
Intent-to-Attend	x	x	x	x	x	x	x	x	x	x	x	x	x	x	x	x	x	x	x	x	
Food Diaries	x ¹																				

ET= Early Termination. Vitals = weight, waist circumference, blood pressure, pulse, and Dual X-Ray Absorptiometry (i.e., body composition). ** Includes lipid profile (i.e., cholesterol, triglycerides), metabolic panel (i.e., blood urea nitrogen (BUN), creatinine (Cr), electrolytes, blood glucose level), complete blood count (CBC), and thyroid stimulating hormone (TSH). C reactive protein (CRP) and inflammatory marker panels (Human TH1/TH2 10-Plex (IFN-g, IL-1b, IL-2, IL-4, IL-5, IL-8, IL-10, IL-12p70, IL-13, TNF-a)) will be included at pre- and post-treatment visits. A urine pregnancy test will be administered at Week 0 to determine eligibility.

¹As needed.

D. Independent Evaluator Training

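### Patients who move from TAU to NEW Tx start exercise and diet at about Week 21 on safety screens that the plan schedules only at Week 0

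*Combined protocol and SAP*

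**What the plan says.** **Crossover.** Section IV.A.ii offers NEW Tx to TAU patients "who complete the first 20 weeks of the study will have the option to receive NEW Tx". Those who accept "will follow the same procedures as the NEW Tx group over an additional 20 weeks". The same sentence goes on to explain this as assessments at Weeks 30, 40 and 52 and points to Table 2.

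**Exclusions that guard the intervention.** Section IV.B.ii excludes anyone with "Endorsed item, confirmed by patient's physician, on the PAR-Q", anyone pregnant by urine test, and anyone with "Contraindications to exercise or diet interventions (e.g., co-morbid nutritional and metabolic diseases, physical injuries"). Section IV.C.xi says the PAR-Q "is a seven-item, self-report questionnaire to screen individuals for starting an exercise program".

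**Timing of the screens.** Table 1 marks the PAR-Q once, at Week 0. Table 2 begins at Week 21 and has no PAR-Q row. The footnotes of both tables carry the sentence "A urine pregnancy test will be administered at Week 0 to determine eligibility". Section IV.B requires an EKG in participants over 40 where clinically indicated and gives no week. The Table 1 footnote places it at Week 0, for those aged 40 or more, and the Table 2 footnote does not mention it.

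**Other safety data near crossover.** Section IV.B schedules a fasting blood draw at Week 20. Table 1 has vitals, CGI-BP, CMF and MADRS at about the same time. Section VI.B.ii has the MADRS suicide item monitored throughout Phase II, and Section VI.B.iii allows withdrawal when investigators see substantial risk.

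**The concern.** The plan treats a physician-confirmed PAR-Q item, pregnancy, and contraindications to exercise or diet as reasons not to give this intervention. A crossover patient begins that same intervention at about Week 21. It includes a daily calorie goal (Section III.A) and weekly goals that build toward moderate exercise on five days a week (Section III.B). Yet the schedule has no clear point at which those exclusions are checked again before the first session.

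A pregnancy, an injury or a new cardiac symptom arising during the 20 weeks of TAU would be found only if the patient mentioned it or if it showed in data collected for another purpose. What is at stake is the safety of individual patients in the extension, not an estimate or a test.

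**Working it through.** The plan states no figure on this point, so the check compares the schedules and then takes a subtraction.

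**Step 1. Set the schedules side by side.**

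| Screen | Table 1 (NEW Tx and TAU) | Table 2 (waitlist, Weeks 21 to 52) |
|---|---|---|
| PAR-Q | One mark, Week 0 | No row |
| Urine pregnancy test | Footnote: Week 0 | Same sentence, Week 0, which is not a column |
| EKG | Footnote: Week 0 | Not mentioned |
| Medical history | One mark, Week 0 | No row |

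Some Table 1 columns are shifted in the extracted text. A row with a single mark and a row that is absent are not affected by that.

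**Step 2. Ask whether anything else scheduled near Week 20 does the same job.**
- Blood draw: the listed contents begin "Includes lipid profile (i.e., cholesterol, triglycerides), metabolic panel" and continue through blood count, TSH and inflammatory markers. No pregnancy test is among them.
- Exercise Questionnaire: it "assesses baseline (i.e., past) exercise history as well as ongoing exercise duration and frequency at follow-up study visits". That is history and amount of exercise, not readiness for it.
- CGI-BP, MADRS and CMF cover illness severity, mood and medication.
- EKG: the rule in Section IV.B has no week, but the Table 1 footnote fixes it at Week 0, so it should not be counted as a safeguard at crossover.
- No rule requires the Week 20 results to be reviewed before the first NEW Tx session.

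**Step 3. Age of the Week 0 screens.** The Week 21 start is inferred from the first column of Table 2 and from the additional 20 weeks ending at Week 40. The randomized arm is taken to start at Week 1.
- First session, crossover: 21 − 0 = 21 weeks.
- First session, randomized to NEW Tx: 1 − 0 = 1 week.
- End of treatment, crossover: 40 − 0 = 40 weeks.
- End of treatment, randomized to NEW Tx: 20 − 0 = 20 weeks.

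A crossover patient therefore starts on screens older (21 weeks) than those of a randomized patient who is finishing (20 weeks).

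**Step 4. Number of patients.** Phase II is given as n = 40 in Section II and n = 60 in Section IV, with 1:1 allocation, so TAU has 40/2 = 20 or 60/2 = 30 patients. The plan expects about 80% retention: 20 × 0.80 = 16 and 30 × 0.80 = 24 would be offered NEW Tx. The documents give no uptake. Assuming 50% to 100%, the number starting is 16 × 0.5 = 8 up to 24 × 1.0 = 24.

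**Step 5. After the fix.** With the screens repeated at Week 20 or 21, their age at a Week 21 start is 21 − 20 = 1 week or 21 − 21 = 0 weeks.

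**The case against.** **The commitment to the same procedures could bring the Week 0 screens with it.** This is the best counter-reading, and it has most force for the pregnancy test. The Table 2 footnote is not a straight copy of Table 1's: the height timing and the EKG sentence were removed, but the pregnancy sentence stayed, in a table that applies only to waitlist patients. The test may have been intended at the start of waitlist treatment, with the week label left uncorrected. A reader might infer that the plan definitely omits the test; the text does not settle that. The PAR-Q half is firmer, because Table 2 has no row for it and the text explains the shared procedures as three later assessments.

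**There is no standard for a stale screen.** The documents give no validity period for a PAR-Q and do not say why pregnancy is excluded. Randomized patients also go through treatment without a repeat. This stands: a reader might infer that 21 weeks exceeds some accepted limit, and the documents do not support that. The narrower point survives, because the PAR-Q is described as a screen for starting exercise and these patients start at Week 21.

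**The risk is small and patients are watched.** Section III.B presents exercise as casual lifestyle activity, modules are chosen to suit the individual, therapists have weekly supervision, and the DSMB receives quarterly reports. The Week 20 bloods are drawn for clinical monitoring. A reader might infer that crossover patients have no safety oversight; that would be wrong. These safeguards nevertheless depend on a problem already having come to light, and none of them is a PAR-Q or a pregnancy test.

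**Conclusion.** The point holds as a modest patient-safety gap in the optional extension. As the plan is written, the PAR-Q, the pregnancy test and the EKG are about 21 weeks old when a crossover patient starts NEW Tx, against about 1 week for a randomized patient. Confidence is high for the PAR-Q. For the pregnancy test the fault is either a missing test or a wrong week label, and either needs correcting.

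The interval assumes first sessions at Week 21 and Week 1. The 8 to 24 patients concerned rest on the planned 80% retention and an assumed uptake of 50% to 100%. The documents give no rates for new PAR-Q problems or pregnancies, so no expected number of harms can be stated.

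A reader might also infer that the trial's results are compromised. They are not: crossover follows the randomized 20-week comparison, and no analysis in Section VIII.B names the waitlist group.

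**What to change.** - Add a pre-treatment entry (Week 20/21) to Table 2 with the PAR-Q, the urine pregnancy test for women who could be pregnant, and the EKG rule applied again (participants aged 40 or over, where clinically indicated).
- Correct the Table 2 footnote so that the pregnancy test is placed at that time point.
- State in Section IV.A.ii that, before the first NEW Tx session, the PAR-Q exclusion (physician-confirmed item), the pregnancy exclusion and the contraindication exclusion must be clear, and the existing Week 20 MADRS suicide item must have been reviewed.

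The cost is one seven-item form per crossover patient and one urine test per woman to whom it applies, with an EKG only where indicated. A contact already exists: the Week 20 visit, or Week 21, when Table 2 marks the URICA and metabolic cart. The downside is that a few patients may be deferred or found ineligible, so the offer of NEW Tx after TAU becomes conditional.
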